Study information

Title	Administration of ELranaTamab In the Real-World: Treatment Patterns, Healthcare Resource Utilization, Costs, Effectiveness, anD SafEty (ALTITUDE-2)			
Protocol number	C1071044			
Protocol version identifier	V 2.0			
Date	6 August 2025			
EU Post Authorization Study (PAS) register number	EUPAS1000000293			
Active substance	L01FX32. Elranatamab			
Medicinal product	$ELREXFIO^{TM}$			
Research question and objectives	The overall research question of this study is to describe the real-world usage of elranatamab.			
	The specific objectives are as follows:			
	 Primary Objective 1: To describe the demographics, clinical history, and treatment history of patients treated with elranatamab 			
	Objective 2: To describe the administration and treatment management of elranatamab			
	Objective 3: To describe all-cause and MM-related healthcare resource utilization (HCRU) and associated costs among patients treated with elranatamab			
	Exploratory			
	• Exploratory Objective 1: To describe the tolerability and real-world safety of elranatamab			
	• Exploratory Objective 2: To describe the overall effectiveness of elranatamab in terms of time to next treatment or death (TTNT/D) and overall survival (OS) Exploratory Objective 3: In a separate cohort, replicate all			
Country(ies) of study	objectives for patients who initiated teclistamab United States			
country (100) or study				

This document contains confidential information belonging to Pfizer. Except as otherwise agreed to in writing, by accepting or reviewing this document, you agree to hold this information in confidence and not copy or disclose it to others (except where required by applicable law) or use it for unauthorized purposes. In the event of any actual or suspected breach of this obligation, Pfizer must be promptly notified.

1. TABLE OF CONTENTS 2. LIST OF ABBREVIATIONS......5 5. AMENDMENTS AND UPDATES......11 7. RATIONALE AND BACKGROUND......15 8. RESEARCH OUESTION AND OBJECTIVES16 9.2.2. Exclusion Criteria 18 9.6. Data Management40 9.7.1. Descriptive Analysis41 9.8. Quality Control......44 9.9. Limitations of the Research Methods......44 10. PROTECTION OF HUMAN PARTICIPANTS45

ELREXFIOTM (elranatamab) C1071044 NON-INTERVENTIONAL STUDY PROTOCOL V2.0, 6 August 2025

10.3. Institutional Review Board (IRB)/Ethics Committee (EC)	46
10.4. Ethical Conduct of the Study	46
11. MANAGEMENT AND REPORTING OF ADVERSE EVENTS/ADVERSE REACTIONS	46

2. LIST OF ABBREVIATIONS

Abbreviation	Definition
AE	Adverse Event
BCMA	B-Cell Maturation Antigen
BsAb	Bispecific Antibody
CAR-T	Chimeric Antigen Receptor T-Cell Therapy
CCI	Charlson Comorbidity Index
CI	Confidence Interval
CMS	Centers for Medicare and Medicaid Services
CPT	Current Procedural Terminology
CRS	Cytokine Release Syndrome
DoR	Duration of Response
EC	Ethics Committee
ED	Emergency Department
ESRD	End-Stage Renal Disease
FDA	Food and Drug Administration
FFS	Fee for Service
GPP	Good Pharmacoepidemiology Practices
HCPCS	Healthcare Common Procedure Coding System
HCRU	Healthcare Resource Utilization
ICANS	Immune Effector Cell-Associated Neurotoxicity Syndrome
ICD-10	International Classification of Diseases, 10th Edition
IMiDs	Immunomodulatory Drugs
IP	Inpatient
IQR	Interquartile Range
IRB	Institutional Review Board
mAbs	Monoclonal Antibodies
MG	Milligram
MM	Multiple Myeloma
NDC	National Drug Code

NCCN	National Comprehensive Cancer Network
ОР	Outpatient
ORR	Objective Response Rate
OS	Overall Survival
PIs	Proteasome Inhibitors
РЈР	Pneumocystis Jiroveci Pneumonia
PPPM	Per-Person-Per-Month
RAI	Relative Administration Intensity
RDI	Relative Dose Intensity
RRMM	Relapsed And Refractory Multiple Myeloma
SAP	Statistical Analysis Plan
SD	Standard Deviation
SDoH	Social Determinants of Health
TTD	Time to Discontinuation
TTNT/D	Time To Next Treatment/Death
US	United States
VRDC	Virtual Research Data Center

4. ABSTRACT

Title: Administration of ELrana Tamab In the Real-World: Treatment Patterns, Healthcare Resource Utilization, Costs, Effectiveness, anD SafEty (ALTITUDE-2)

Version: v2.0

Date: 6 August 2025

Author: Redacted

Rationale and background: Multiple Myeloma (MM) is a hematological malignancy characterized by the proliferation of malignant plasma cells within the bone marrow. This cancerous growth disrupts the normal production of blood cells, leading to weakened immune function, anemia, bone pain, and increased susceptibility to infections. MM accounts for approximately 1% of all cancers and.

Elranatamab is a B-cell maturation antigen (BCMA) bispecific antibody (BsAb) that was approved in the United States (US) for patients with MM who have been treated with at least four lines of therapy, including a proteasome inhibitor (PIs), an immunomodulatory agent (IMiD), and an anti-CD38 monoclonal antibody (mAb). This study will describe the real-world usage, patient outcomes, and healthcare resource utilization (HCRU) associated with elranatamab in the US by leveraging up-todate Medicare Fee for Service (FFS) data. An exploratory objective seeks to describe the real-world usage another approved BCMA BsAb, teclistamab.

Research question and objectives: This study aims to describe the real-world usage of elranatamab for the treatment of RRMM. To meet these objectives, the Clarify team will partner with Pfizer to create a curated dataset of Medicare FFS beneficiaries to serve as the foundation upon which to generate descriptive data.

The overall research question of this study is to describe the real-world usage of elranatamab. Specifically, the analysis will focus on the following primary research objectives:

Primary

- **Objective 1:** To describe the demographics, clinical history, and treatment history of patients treated with elranatamab
- **Objective 2:** To describe the administration and treatment management of elranatamab
- Objective 3: To describe all-cause and MM-related HCRU and associated costs among patients treated with elranatamab

Exploratory

- Exploratory Objective 1: To describe the tolerability and real-world safety of elranatamab
- Exploratory Objective 2: To describe the overall effectiveness of elranatamab in terms of time to next treatment or death (TTNT/D) and overall survival (OS)
- Exploratory Objective 3: In a separate cohort, replicate all objectives for patients who initiated teclistamab

Study Design: This will be a retrospective, non-interventional descriptive cohort study using deidentified patient data from US-based Medicare FFS beneficiaries. The study will utilize claims data from the Centers for Medicare and Medicaid Services (CMS), spanning from 2016 through December 2025.

Population: This study will include adult (≥18 years old) patients with an International Classification of Diseases, tenth revision (ICD-10) code for RRMM (defined as MM ICD-10 codes: C90.0x). The study cohort will include patients with RRMM who initiate elranatamab between August 14, 2023 (US approval date for elranatamab) and March 2025. The index date for patients will be defined as the date of the first prescription or medical claim for elranatamab. Patients will be required to have at least 180 days of continuous closed-claims enrollment before the index date and 30 days after the index date. Select exploratory analyses will also include a teclistamab-exposed cohort.

Variables: Based on the study cohorts of interest, patients may be characterized by the following attributes of interest:

- Demographic characteristics such as age, sex, race/ethnicity, state, and region
- Social determinants of health such as household income, education level, marital status, and homeownership
- Clinical characteristics such as comorbidities or past treatment status
- Healthcare resource utilization such as hospitalization and place of service distribution

Prior treatment history will be captured based on the use of National Comprehensive Cancer Network (NCCN) guideline-recommended treatments, which include chimeric antigen receptor T cell therapy (CAR-T), PIs, and IMiDs.

HCRU and costs will be described overall and by place of service, including inpatient (IP) visits, outpatient visits (OP, defined as non-IP/non-ED), emergency department (ED) visits, and pharmacy claims. Additionally, HCRU and associated costs will be reported as all-cause and MM-related.

Adverse events will include cytokine release syndrome (CRS), immune effector cell-associated neurotoxicity syndrome (ICANS), peripheral neuropathy, and infections. Effectiveness outcomes will include TTNT/D and OS.

Data Sources: This study will use 100% Medicare FFS claims data (including parts A, B and D) accessed through the Virtual Research Data Center (VRDC) from 2016 through December 2025.

Study Size: As of August 2024, the dataset included 133 patients with a claim for elranatamab. To further assess whether sufficient sample size is available to proceed with the study, a power analysis will be completed to assess estimates of precision for a one sample means.

Data Analysis: This study will be largely descriptive in nature, and no formal statistical comparisons will be performed. The number of patients who meet study eligibility criteria will be summarized in an attrition table. Inclusion and exclusion criteria will be listed hierarchically and the number of patients remaining at each step will be reported. Patient and treatment characteristics will be

summarized using descriptive statistics. Categorical variables will be summarized by the number of available observations, frequency, percentage, and 95% confidence limits. Continuous variables will be summarized by the number of available observations, mean, standard deviation, 95% confidence limits, median, quartiles, minimum, and maximum, where appropriate. The prevalence and incidence, as well as the associated 95% confidence intervals (CI) for each adverse event, will be estimated. Kaplan-Meier methods will be used to estimate the median time to event, including 95% CIs for TTNT/D and OS.

Milestones: Data analysis will begin 1 October 2024 and end 4 June 2025. An interim set of results will be delivered 18 December 2024 using data through September 2024. Additional interim results will be delivered in September 2025 (based on June 2025 data) and in December 2025 (based on September 2025 data) with a final analysis to be delivered in February 2026 (based on December 2025 data). A final report will be delivered in May 2026 based on this final analysis.

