9.2.1. Inclusion Criteria

Patients must meet all of the following inclusion criteria to be eligible for inclusion in the study:

- At least 1 observed prescription claim or medical claim for elranatamab or teclistamab in the
 dataset between August 14, 2023, and the most current date of data available. The index date will
 be the date of an individual's first claim. Patients who have received teclistamab before the
 August 14, 2023, date will require a period (i.e., 6 or 12 months) without a claim for teclistamab.
- 2. Age 18 or older on index date

- 3. Diagnosis of RRMM (defined as MM) any time prior to index date
- 4. At least 180 days of continuous closed-claims medical and pharmacy enrollment prior to index (inclusive) and 30 days post-index

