9.3. Variables

Table 1 includes definitions and assessment periods for all study variables that will be used as eligibility criteria. The full code list can be found in ANNEX 2. ADDITIONAL INFORMATION.

Table 1. Variables Used to Determine Eligibility

Variable	Operational Definition	Assessment Period
Elranatamab	Prescription claim or medical claim with a National Drug Code (NDC), Healthcare Common Procedure Coding System (HCPCS), International Classification of Diseases, 10th Edition (ICD-10) code or generic name in the inpatient, non-inpatient or pharmacy setting for elranatamab	Index event
Teclistamab	Prescription claim or medical claim with an NDC, HCPCS, ICD-10 code or generic name in the inpatient, non-inpatient or pharmacy setting for teclistamab	Index event
Age	Age is greater than or equal to 18 years and is not missing	Index date
MM diagnosis	Medical claim in the inpatient or non-inpatient setting with an ICD-10 code for MM	All available data to index date
Observability	Closed-claims medical and pharmacy enrollment	180 days prior to index date to index date (inclusive) and 30 days post index
Medicare entitlement	Reason for Medicare entitlement	Index date

Table 2 includes definitions and assessment periods for all study variables that will be used as baseline and treatment characteristics. The full code list can be found in ANNEX 2. ADDITIONAL INFORMATION. If applicable, the frequency and percentage of patients with missing data for each variable will be described.

Table 2. Variables Used to Determine Baseline and Treatment Characteristics

Objective	Variable	Definition	Assessment Period(s)
1	Age	Age in years (continuous). Age will be calculated using the birth year variable from the beneficiary enrollment information.	Index date
1	Sex (assigned at birth)	Categorical sex	Index date
1	Race/Ethnicity	Beneficiary enhanced race/ethnicity designation based on first and last name algorithms and the Social Security Administration race code (modified using the Research Triangle Institute algorithm). Categorical race and ethnicity Caucasian African American Asian or Pacific Islander Hispanic or Latino Other Unknown	Index date
1	US Census Region	Categorical region, assessed as the most recent value from index date Northeast Midwest West South Unknown	Index date
1	State	State of residence	Index date

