Exploratory Obj 1	Cytokine release syndrome (CRS) ¹	Medical claim with an ICD-10 code in the inpatient, non-IP or pharmacy setting for CRS, categorized into the following grades (categorical): • Any (all grades and unspecified grade) • Grade 1 • Grade 2 • Grade 3 • Grade 4 • Grade 5 If patients have multiple, conflicting grades, then the highest recorded grade will be reported	Index date to end of follow-up, where follow-up will be based on last dose of elranatamab or teclistamab (e.g., 14 days after last recorded dose or 90 days after last recorded dose).
Exploratory Obj 1	Cytokine release syndrome (CRS) ¹ symptoms	Medical claim with an ICD-10 code in the inpatient, non-IP or pharmacy setting for CRS symptoms, per a algorithmic type approach (e.g., Keating algorithm, identifying patients with fever, hypotension, fatigue, headaches, hypoxia)	Index date to end of follow-up, where follow-up will be based on last dose of elranatamab or teclistamab (e.g., 14 days after last recorded dose or 90 days after last recorded dose).
Exploratory Obj 1	Immune effector cell-associated neurotoxicity syndrome (ICANS)	Medical claim with evidence of an ICD-10 code in the inpatient, non-IP or pharmacy setting for ICANS, categorized into the following grades (categorical): • Any (all grades and unspecified grade) • Grade 1 • Grade 2 • Grade 3 • Grade 4 • Grade 5 If patients have multiple, conflicting grades then the highest recorded grade will be reported	Index date to end of follow-up, where follow-up will be based on last dose of elranatamab or teclistamab (e.g., 14 days after last recorded dose or 90 days after last recorded dose).
Hematologic	events		
Exploratory Obj 1	Anemia ¹	Medical claim with an ICD-10 code in the inpatient, non-IP, or pharmacy setting for anemia (dichotomous)	Index date to end of follow-up, where follow- up will be based on last dose of elranatamab or teclistamab (e.g., 14 days after last recorded dose or

			90 days after last recorded dose).
Exploratory Obj 1	Lymphopenia ¹	Medical claim with an ICD-10 code in the inpatient, non-IP, or pharmacy setting for lymphopenia (dichotomous)	Index date to end of follow-up, where follow-up will be based on last dose of elranatamab or teclistamab (e.g., 14 days after last recorded dose or 90 days after last recorded dose).
Non-hematol	ogic events		

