Exploratory Obj 1	Other pneumonia ²	Medical claim with an ICD-10 code in the inpatient, non-IP, or pharmacy setting for pneumonia other than adenoviral or cytomegaloviral pneumonia (dichotomous)	Index date to end of follow-up, where follow-up will be based on last dose of elranatamab or teclistamab (e.g., 14 days after last recorded dose or 90 days after last recorded dose).
Exploratory Obj 1	Upper respiratory tract Infection ²	Medical claim with an ICD-10 code in the inpatient, non-IP, or pharmacy setting for upper respiratory tract infection (dichotomous)	Index date to end of follow-up, where follow-up will be based on last dose of elranatamab or teclistamab (e.g., 14 days after last recorded dose or 90 days after last recorded dose).
Exploratory Obj 1	Sepsis ²	Medical claim with an ICD-10 code in the inpatient, non-IP, or pharmacy setting for sepsis (dichotomous)	Index date to end of follow-up, where follow-up will be based on last dose of elranatamab or teclistamab (e.g., 14 days after last recorded dose or 90 days after last recorded dose).
Exploratory Obj 1	Cytomegaloviral infection ²	Medical claim with an ICD-10 code in the inpatient, non-IP, or pharmacy setting for cytomegaloviral infection (dichotomous)	Index date to end of follow-up, where follow- up will be based on last dose of elranatamab or teclistamab (e.g., 14 days after last recorded dose or

			90 days after last recorded dose).
Exploratory Obj 1	PJP ²	Medical claim with an ICD-10 code for PJP (dichotomous)	Index date to end of follow-up, where follow-up will be based on last dose of elranatamab or teclistamab (e.g., 14 days after last recorded dose or 90 days after last recorded dose).
Exploratory Obj 1	Hepatitis C ²	Medical claim with an ICD-10 code in the inpatient, non-IP or pharmacy setting for hepatitis C (dichotomous)	Index date to end of follow-up, where follow-up will be based on last dose of elranatamab or teclistamab (e.g., 14 days after last recorded dose or 90 days after last recorded dose).
Exploratory Obj 1	Hepatitis B ²	Medical claim with an ICD-10 code in the inpatient, non-IP or pharmacy setting for hepatitis B (dichotomous)	Index date to end of follow-up, where follow-up will be based on last dose of elranatamab or teclistamab (e.g., 14 days after last recorded dose or 90 days after last recorded dose).

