9.7.6. Tolerability

The prevalence and incidence for each adverse event (Table 3) will be estimated. All prevalence and incidence estimates will be reported as a percent with corresponding 95% CIs.

Prevalance =
$$(\frac{No.\ of\ patients\ with\ an\ event}{Total\ number\ of\ patients\ in\ the\ cohort})\ x\ 100$$

For the incidence analysis, only patients who did not have the event prior to their index date will be included. The length of the washout is dependent on the outcome (see Table 3).

$$Incidence = \left(\frac{\text{No. of patients with an event that did not have an event in baseline}}{\text{Total number of patients in the cohort}}\right) x \ 100$$

PFIZER CONFIDENTIAL

Patients will be assessed over two time periods: from the index date until 14 days or 90 days after their last administration of the index medication.

Additionally, the time to infection onset will be assessed using unadjusted Kaplan-Meier methods. The median time to event in days will be reported along with the IQR. The 95% CIs for the median time to event will be calculated using log-log transformation.

Patients will be censored at the earliest of death, next treatment (CAR-T, BsABs, bendamustine or belantamab), the end of part A or B continuous closed-claim coverage, or the end of data.

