ANNEX 2. ADDITIONAL INFORMATION

			Codes
Variable	Role	Data Source(s)	
Elranatamab	Inclusion criteria	Claims data	HCPCS: C9165, J1323 NDC: 00069449401, 00069449402, 00069252201, 00069252202 ICD-10 Procedure code: XW013L9 Generic name: Elranatamab
Teclistamab	Inclusion criteria	Claims data	HCPCS: J9380, C9148 NDC: 57894044901, 57894045001 ICD-10 Procedure code: XW013487Generic name: Teclistamab
Multiple Myeloma	Inclusion criteria, Outcome - HCRU	Claims data	C90.0x
Age	Inclusion criteria, Baseline characteristic - Demographic	Claims data	N/A
Sex	Baseline characteristic - Demographic	Claims data	N/A

Dagg/Etlan! -: t	Baseline	Claims	N/A
Race/Ethnicity	characteristic - Demographic	data data	N/A
US Census Region	Baseline characteristic - Demographic	Claims data	N/A
State	Baseline characteristic - Demographic	Claims data	- N/A
BCMA-directed therapy	Baseline characteristic - Treatments, Outcome - HCRU	Claims data	CPT: 0537T, 0538T, 0539T, 0540T HCPCS: C9081, C9098, Q2055, Q2056, J9037, C9069 NDC: 57894011101, 57894011102, 59572051501, 59572051502, 59572051503, 00173089601 Generic names: Idecabtagene Vicleucel, Ciltacabtagene Autoleucel, Belantamab ICD10PCS: XW033K7, XW043K7, XW043A7, XW043A7, XW033A7
CAR-T	Baseline characteristic - Treatments, Outcome - HCRU	Claims data	CPT: 0537T, 0538T, 0539T, 0540T HCPCS: C9081, C9098, Q2055, Q2056 NDC: 57894011101, 57894011102, 59572051501, 59572051502, 59572051503 Revenue codes: 0871, 0872, 0873, 0874, 0891 ICD10PCS: XW033C7 XW033G7 XW033J7 XW033K7 XW043C7 XW043G7 XW043K7 Generic names: Idecabtagene Vicleucel, Ciltacabtagene Autoleucel
Hematopoietic stem cell transplantation	Baseline characteristic - Treatments	Claims data	CPT: 38240, 38241, 38242, 38243 HCPCS: A52879, S2150 ICD-10 Diagnosis: T86.0, T86.00, T86.01, T86.02, T86.03, T86.09, T86.5, Z48.290, Z94.81, Z94.84 ICD-10 Procedure: 30240Y0, 30243Y0, 30250Y0, 30253Y0, 30260Y0, 30263Y0, 30230Y1, 30233Y1, 30240Y1, 30243Y1, 30230Y2, 30233Y2, 30240Y2, 30243Y2, 30230Y3, 30233Y3, 30240Y3, 30243Y3, 30230Y4, 30233Y4, 30240Y4, 30243Y4, 30253Y1, 30260Y1, 30263Y1, 30233X0,

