Use of premedication	Outcome - Dosing and Administration Patterns	Claims data	HCPCS: J1094, J1096, J8540, J1100, J0131, J7637, J7638, J7312, J1200, Q0163 Generic names (and associated NDCs): Acetaminophen, Dexamethasone, Diphenhydramine
Inpatient	Baseline characteristic, Outcome - HCRU	Claims data	Any event in the inpatient table or an event in the non-inpatient table where acute_subacute is "acute inpatient" or where utilization type is "professional services", and service subcategory contains the term "hospital/IP encounter"
Outpatient	Baseline characteristic, Outcome - HCRU	Claims data	Any event in the non-inpatient table where utilization type is outpatient and service subcategory is not "emergency dept encounter"

Emergency department	Baseline characteristic, Outcome - HCRU	Claims data	Any event in the non-inpatient table where utilization type is "outpatient" and service subcategory is "emergency dept encounter"
Cytokine release syndrome (CRS)	Safety events	Claims data	ICD-10 Diagnosis: D89.83x
Immune effector cell- associated neurotoxicity Syndrome (ICANS)	Adverse events	Claims data	ICD-10 Diagnosis: G92.0x
Anemia	Adverse events	Claims data	ICD-10 Diagnosis: D46.0, D46.1, D46.20, D46.21, D46.22, D46.4, D46.9, D46.A, D46.B, D46.C, D46.Z, D47.4, D50.0, D50.1, D50.8, D50.9, D51.0, D51.1, D51.2, D51.3, D51.8, D51.9, D52.0, D52.1, D52.8, D52.9, D53.0, D53.1, D53.2, D53.8, D53.9, D55.0, D55.1, D55.2, D55.21, D55.29, D55.3, D55.8, D55.9, D59.0, D59.1, D59.10, D59.11, D59.12, D59.13, D59.19, D59.2, D59.3, D59.30, D59.31, D59.39, D59.4, D59.5, D59.6, D59.8, D59.9, D60.0, D60.1, D60.8, D60.9, D61.01, D61.09, D61.1, D61.2, D61.3, D61.810, D61.811, D61.818, D61.82, D61.89, D61.9, D63.0, D63.1, D63.8, D64.9, D75.81
Lymphopenia	Adverse events	Claims data	ICD-10 Diagnosis: D72.810
Hypogammaglobulinemia	Adverse events	Claims data	ICD-10 Diagnosis: D80.1, D80.3, D80.9
Hypophosphataemia	Adverse events	Claims data	ICD-10 Diagnosis: E83.39
Hypokalaemia	Adverse events	Claims data	ICD-10 Diagnosis: E87.6
Arthralgia	Adverse events	Claims data	ICD-10 Diagnosis: M25.5x
Pyrexia	Adverse events	Claims data	ICD-10 Diagnosis: R50.x
Hypotension	Adverse events	Claims data	ICD-10 Diagnosis: I95.0, I95.81, I95.89, I95.9, I95.2
Fatigue	Adverse events	Claims data	ICD-10 Diagnosis: R53.x, G93.3x

Nausea or vomiting	Adverse events	Claims data	ICD-10 Diagnosis: R11.x
Diarrhea	Adverse events	Claims data	ICD-10 Diagnosis: R19.7, K59.1

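### Diagnoses on an inpatient index claim count as post-index adverse events even if present before the first dose, which can inflate incidence and add day-0 infections

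*Protocol*

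**What the plan says.** Index date. The abstract reads: "The index date for patients will be defined as the date of the first prescription or medical claim for elranatamab". Inclusion criterion 1 in section 9.2.1 agrees that it will "be the date of an individual's first claim". Table 1 lets the qualifying claim be one with a "code or generic name in the inpatient, non-inpatient or pharmacy setting for elranatamab", and Annex 2 lists an inpatient procedure code among the identifiers ("ICD-10 Procedure code: XW013L9"). Table 2 also records care setting, inpatient included, on the index date.

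Adverse events. Table 3 defines nearly all of them alike. For sepsis the definition is "Medical claim with an ICD-10 code in the inpatient, non-IP, or pharmacy setting for sepsis (dichotomous"), with no condition on diagnosis position or present-on-admission status. The window is "Index date to end of follow-up, where follow-up will be based on last dose of elranatamab or teclistamab"; section 9.7.6 repeats it as "from the index date until 14 days or 90 days after their last administration of the index medication".

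Incidence. Section 9.7.6 restricts incidence to patients without the event before the index date. The Table 3 footnotes set washouts of 30 days (for example CRS, anemia, hepatotoxicity), 60 days (infections, renal failure) and 14 days (for example pyrexia, hypotension, fatigue).

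Baseline. MM-related comorbidities are assessed up to the day before index (section 9.2). The Charlson window runs through the index date itself.

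**The concern.** An inpatient claim describes a hospital stay. Its diagnosis list can hold the reason for admission, long-standing disease and complications of treatment together. The adverse event rule does not separate these. If the claim carries the index date, all of them enter the post-index window, and any not coded elsewhere during the washout is reported as incident.

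Two outputs of Exploratory Objective 1, and of its teclistamab replication under Exploratory Objective 3, are at stake. Incidence percentages may include conditions that preceded exposure. Time to infection onset, a Kaplan-Meier analysis from index, may gain day-0 infections that came before the first dose. More patients would narrow the confidence intervals but leave this bias unchanged. The limitations in section 9.9 cover rule-out coding and data-entry errors, not this.

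**Working it through.** The plan gives no adverse event rate or inpatient-start share that bears on this, so there is no figure to reproduce. The check is a reading of the rules, followed by an illustration of size.

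**Step 1: follow one diagnosis through the rules.** Take a patient whose first drug claim is inpatient and whose stay also carries an infection code.
- Index = date of that claim (abstract, 9.2.1).
- The infection code is a listed ICD-10 code in an inpatient setting, so it meets the event definition (Table 3).
- If it is dated on the index date, it is inside the window (Table 3, 9.7.6).
- It is not before the index date, so it does not exclude the patient from incidence (9.7.6).
- If no claim in the previous 60 days carries the code, the washout does not act.
- Result: an incident infection, with onset on day 0.

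**Step 2: what the washout leaves.** Several event lists in Annex 2 contain chronic codes: N18x and Z99.2 under renal failure, B18.1 and B18.2 under hepatitis B and C. A chronic condition not billed in the previous 60 days but listed on the index stay becomes incident.

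**Step 3: the index day sits on both sides.** The Charlson window includes the index date, and so does the event window. The Annex 2 lists overlap:
- N18, N19 and Z99.2: Charlson renal disease and event renal failure.
- K71.1x, K71.3, K71.4, K71.5 and K71.7: Charlson liver disease and event hepatotoxicity (K71.x).

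One index-day code can thus be a baseline comorbidity and an adverse event.

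**Step 4: illustrative size.** Let h be the share of patients indexed on an inpatient claim, and q the share of those with a given condition present on admission and not coded in the washout. Both are assumptions. Excess incidence = h × q; excess cases = 133 × h × q, where 133 is the August 2024 count in section 9.5. The denominator is the whole cohort, as the formula in 9.7.6 prints it.

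| h | q = 0.02 | q = 0.05 | q = 0.10 |
|---|---|---|---|
| 0.25 | 0.5 points (0.7 cases) | 1.25 (1.7) | 2.5 (3.3) |
| 0.50 | 1.0 (1.3) | 2.5 (3.3) | 5.0 (6.7) |
| 0.75 | 1.5 (2.0) | 3.75 (5.0) | 7.5 (10.0) |

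For scale, the 95% Wald half-width is 1.96 × √(p(1 − p)/133): 3.7 points at p = 0.05 and 5.1 points at p = 0.10.

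**Step 5: common events.** A patient who later has a true event already counts once, so under independence the net excess is h × q × (1 − p). Taking the elranatamab trial rates in section 7 as illustrative p:
- Infections, p = 0.699: 0.5 × 0.301 = 0.15 to 7.5 × 0.301 = 2.3 points.
- Anemia, p = 0.488: 0.5 × 0.512 = 0.26 to 7.5 × 0.512 = 3.8 points.

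This reduction does not protect time to infection onset, because a false day-0 infection replaces the later true onset.

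**The case against.** **The direction is not established.** A reader might infer that inpatient claims are dated from admission and that the bias must be upward. The documents do not say which date an inpatient claim or its diagnoses carry. Some text suggests that index was meant as first administration: Table 3 measures time to discontinuation from first administration while 9.7.5 measures it from index, and Table 4 starts step-up dosing on the index date. If index were the administration date and stay diagnoses carried the admission date, index-stay diagnoses would fall before index and true early events could be lost to baseline. This objection stands. It changes the direction, but the same missing rule is the cause.

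**Prevalence.** A reader might infer that prevalence is biased too. Section 9.7.6 defines it as patients with an event over the whole cohort, with no exclusion of existing disease, so counting such conditions is what it does. This objection stands.

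**Not one claim per stay.** The inpatient row of Annex 2 covers "Any event in the inpatient table" and also some records in the non-inpatient table, such as professional services for a hospital encounter. Some inpatient diagnoses may therefore carry their own dates. This limits how many are affected but does not remove the problem for the index claim.

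**It is SAP detail.** Section 9.7 leaves detailed methods to a SAP that is not shown, and the choice of date field could sit there. But the protocol itself fixes a window that includes the index day and accepts any listed code, puts that day in the Charlson window as well, and says in 9.8 that its codes and algorithms will be strictly followed. What it states already yields the miscount.

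**Cohort comparison.** A reader might infer a distorted contrast between the two drugs. No formal between-group comparison is planned, so that is not claimed.

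**Conclusion.** The concern holds for incidence and time to infection onset. As written, diagnoses on an inpatient index claim that fall on the index date are post-index events whether or not they preceded the first dose, and the washout catches only those also coded in the previous 14, 30 or 60 days. The same diagnosis can also enter the Charlson score.

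The size cannot be derived from the documents. With h of 25-75% and q of 2-10%, both assumed, it is about 0.5 to 7.5 points per event, and less for common events. The upper end exceeds the sampling half-width for an event rate of 5-10% in 133 patients; the lower end is well inside it. An upward direction assumes that index-stay diagnoses are dated on or after index. Patients who start outside hospital are unaffected, as are the primary objectives' treatment-pattern, resource-use and cost estimates, apart from the Charlson overlap at baseline.

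**What to change.** 1. In 9.2 and 9.2.1, state one index-date rule for inpatient starts, for example the administration or procedure date, and use it for every outcome. It belongs there and not in 9.7.6, where it would create a second index date for safety only.
2. In 9.7.6, for incidence and time to infection onset, treat index-stay diagnoses flagged present on admission as baseline. Leave prevalence as it is. The flag is assumed to be available in the extract.
3. Reconcile this with the Charlson window, so that an index-day diagnosis is assigned to baseline or to follow-up and not to both.
4. If the flag is not available, keep the main analysis and add a sensitivity analysis that excludes index-claim diagnoses other than CRS, ICANS and the CRS-symptom codes.

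The cost is two short rules and one claims field, or one extra set of tables. The flag will not separate conditions that arise between admission and first dose. The sensitivity analysis also drops some true early events, so it should be reported beside the main estimate, not in place of it. Because it keeps the CRS-symptom codes, it cannot test fever, hypotension or fatigue as separate events.
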